## 2.4.1.2 Multiple assessments within visit windows

Group 5: PK blood collection Group 6: Immunogenicity Group 7: Vital Signs

The mapping described above applies to all visits (not just scheduled visits). Repeat and/or unscheduled visits (which will be numbered in the database according to new NCDS standards) will be mapped for analysis purposes in the same way as scheduled visits. This leaves the possibility, then, for *multiple assessments* within a particular visit window. The following rules will be used to determine the appropriate measurement to be summarized in the event of multiple assessments within a visit window (See Table 2-2).

\* The first day of administration of randomized study treatment (first dose) is defined as Day 1.

For baseline assessment definition see Section 2.1.1.3. For post-baseline visit windows the following applies (unless otherwise specified):

- for *quantitative variables*, the *closest* to the actual visit is chosen (if two assessments have the same distance, then the earlier one will be chosen);
- for *qualitative variables*, the *worst* record is selected. It is noted that in the analyses performed, *worst* case is always well defined (e.g., for urine protein values "+" and "++", the worst case is defined as "++"),
- in case qualitative variables are based on quantitative variables, the visit will be assigned to the quantitative variable, and this visit will be used for the derived qualitative variable.

Table 2-2 Rules for selecting values for analysis within a given visit window

Timing of measurement	Type of data	Rule
Baseline	All data	See Section 2.1.1.3.
Post-baseline efficacy	All data except for PRO	The measurement closest to the target day will be used. In the event two measurements are taken equally apart (e.g., 1 day before target date and 1 day after), the earlier one will be used.

Timing of measurement	Type of data	Rule
		If two measurements are taken on the same day, then select the first one using eCRF visit number.
		If two measurements have been taken on the same day and same visit then select the worst.
Post-baseline efficacy	PRO data	The measurement closest to the target day will be used. In the event two measurements are taken equally apart (e.g., 1 day before target date and 1 day after), the earlier one will be used.
		If two measurements have been taken on the same day, select the worst.
		If two measurements have the same value, select the first one using eCRF visit number.
Post-baseline safety	Summary visit information (e.g., lab, etc.)	The (non-missing) measurement closest to the target day will be used.
		In the event two measurements are taken equally apart (e.g., 1 day before target date and 1 day after) the first one will be used.
		If two measurements are taken on the same day then select the first one (using the time).
		If two measurements are taken on the same date/time then use the first visit number (assuming this is the planned visit).
		If two measurements are taken on the same date/time/eCRF visit number then use the average of two assessments.
Post-baseline safety	Notable abnormalities (e.g., vital signs) and CTCAE grading for laboratory values	The most extreme measurement in the window will be used. Note this means a participant can have a notably high and notably low measurement within an analysis period.

#### 2.4.2 Prior, concomitant and post therapies

Medications will be identified using the Novartis Drug and Therapy Dictionary (NovDTD) including Anatomical Therapeutic Chemical (ATC) code. Prior and concomitant treatments will be summarized in separate tables by treatment group for the SAF. Concomitant treatments will be displayed by study period as appropriate.

Medications will be presented in alphabetical order, by ATC codes and grouped by anatomical main group (the 1st level of the ATC codes). Tables will show the overall number and percentage of participants receiving at least one treatment of a particular ATC code and at least one treatment in a particular anatomical main group.

Prior medications are defined as treatments taken and stopped prior to first dose of study treatment. Any medication given at least once between the day of first dose of randomized study treatment and within 84 days after last dose will be a concomitant medication, including those which were started before first dose of study treatment and continued into the period where study treatment is administered.

Prior or concomitant medication will be identified by comparing recorded or imputed start and end dates of medication taken to the reference start date. See Section 5.1.3 for details.

Significant prior and concomitant non-drug therapies and procedures will be summarized by primary system organ class and MedDRA preferred term.

Prior non-drug therapies and procedures are defined as non-drug therapies and procedures done prior to first dose of study treatment. Any non-drug therapies and procedures done between the day of first dose of study treatment and within 84 days after last dose will be defined as concomitant non-drug therapies and procedures, including those which were started before first dose of study treatment and continued into the period where study treatment is administered.

The number and percentage of participants receiving prior and concomitant RCT therapy will be presented by randomized treatment group.

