1.3 Schedule of activities (SoA)

The SoA lists all of the assessments when they are performed. All data obtained from these assessments must be supported in the participant's source documentation. The "X" in the table denotes the assessments to be recorded in the clinical database or received electronically from a vendor. The "S" in the table denotes the assessments that are only in the participant's source documentation and do not need to be recorded in the clinical database.

If the Investigator deems it feasible and subject to adequate training, the participants may be able to administer study drug at home (self-administered or administered by caregiver) at Week 1 and Week 3. Participant or caregiver must demonstrate their ability to administer study drug at the BSL visit at the site before home administration is permitted. Tele-visits, i.e., secure videoconferencing, between the Participant and Investigator may also be utilized as additional support for administration of study drug at home.

Participants should be seen for all visits/assessments as outlined in the SoA or as close to the designated day/time as possible. Missed or rescheduled visits should not lead to automatic discontinuation.

Participants who discontinue from study treatment should still attend all visits until End of Study (EOS) as indicated in the SoA.

Participants who discontinue from study should be scheduled for a final evaluation visit (EOT assessments should be performed as final evaluation, or EOS if participant has already completed EOT at Week 16) if they agree, as soon as possible, at which time all of the assessments listed for the EOT visit will be performed. At this final visit, the AEs and concomitant medications not previously reported must be recorded on the Case Report Form (CRF).

Pharmacokinetic samples should be taken prior to study drug administration.

Patient Reported Outcomes (PRO) questionnaires must be completed before any assessments are performed at any given visit.

Repeat or unscheduled samples may be taken for safety reasons or for technical issues with the samples, or unscheduled safety assessments may be performed at the discretion of the Investigator if there is a concern or need follow up for an AE.

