Participants who **disagree to continue attending all remaining study** visits after prematurely discontinuing the study treatment (including those who initially continued to attend site visits but subsequently decided to discontinue the study) should perform an end of treatment visit, 4 weeks after their last study treatment administration (or as soon as possible upon the decision of study discontinuation if more than 4 weeks elapsed since last dose of study treatment). A corresponding end of study post-treatment safety follow up visit should be performed 12 weeks after the last administration of the study treatment (or as soon as possible, if more than 12 weeks elapsed since last dose of study treatment).

If the participant cannot or is unwilling to attend any visit(s), the site staff should maintain regular telephone contact with the participant, or with a person pre-designated by the participant. This telephone contact should preferably be done according to the study visit schedule.

After discontinuation from study treatment, at a minimum, in abbreviated visits, the following data should be collected at clinic visits or via telephone/email contact:

- New / concomitant treatments
- AEs / Serious Adverse Events

The Investigator must also contact the IRT to register the participant's discontinuation from study treatment.

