9.2.3 Treatments

Study treatment

The analysis of study treatment data will be based on the safety set. The number of visits with active and placebo s.c. injections received will be presented by treatment group.

The duration of exposure to study treatment will also be summarized by treatment group. In addition, the number and percentage of participants with cumulative exposure levels (e.g., any exposure, ≥ 1 week, ≥ 2 weeks, ≥ 3 weeks, ≥ 4 weeks, ≥ 8 weeks, etc.) will be presented.

Prior and concomitant medication

Prior and concomitant medications will be summarized in separate tables by treatment group.

Prior medications are defined as treatments taken and stopped prior to first dose of study treatment. Any medication given at least once between the day of first dose of randomized study treatment and the date of the last study visit will be a concomitant medication, including those which were started pre-BSL and continued into the period where study treatment is administered.

Medications will be presented in alphabetical order, by Anatomical Therapeutic Classification (ATC) codes and grouped by anatomical main group. Tables will show the overall number and percentage of participants receiving at least one treatment of a particular ATC code and at least one treatment in a particular anatomical main group.

Significant prior and concomitant non-drug therapies and procedures will be summarized by primary system organ class and Medical dictionary for regulatory activities (MedDRA) preferred term.

Prior surgeries and procedures are defined as surgeries and procedures done prior to first dose of study treatment. Any surgeries and procedures done between the day of first dose of study treatment and within the date of the last study visit will be a concomitant surgeries and procedures, including those which were started pre-BSL and continued into the period where study treatment is administered.

The number and percentage of participants receiving prior and concomitant RCT therapy will be presented by randomized treatment group as well as the reasons for stopping their therapies

(primary lack of efficacy, secondary lack of efficacy, lack of tolerability, other) and the total duration of exposure to RCT therapies previously.

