## 1.1 Study design

CAIN457O12301 is a randomized, double-blind, placebo-controlled Phase III study over 24 weeks in participants with moderate to severe Rotator Cuff Tendinopathy (RCT), refractory to Standard of Care (SoC) (Non-Steroidal Anti-Inflammatory Drugs (NSAIDs) course as per local standard practice, if not intolerant or contraindicated, and a course of physiotherapy over a period of 8 weeks).

A screening period of up to maximum of 56 days will be used to assess participant eligibility. During the 2-week run-in period prior to the Baseline (BSL) visit, the participant will need to have 2 weeks of stable NSAID intake and standardized physiotherapy.

During Study period 1 (BSL to Week 16), double-blinded treatment is administered over 12 weeks, reflecting 16 weeks of total drug exposure. Approximately 234 eligible participants were planned to be randomized at BSL in a 1:1 ratio to one of the following arms:

- Arm 1 (N=117): secukinumab 300 mg s.c. at Day 1 and Weeks 1, 2, 3, 4, 8, and 12
- Arm 2 (N=117): placebo at Day 1 and Weeks 1, 2, 3, 4, 8, and 12

Randomization will be stratified by tear status (no tear/partial tear).

The last dose of study treatment will be administered at Week 12; the primary outcome assessments will be performed at Week 16.

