#### 2.4.1.1 Analysis visit window

Analysis visit windows will be used for the data that is summarized by visit; they are based on the study visit and evaluation schedule and comprise a set of days around the nominal visit day. For any assessment, there are protocol defined scheduled visits around which analysis visit windows were created to cover the complete range of days within the study. Visit windows will vary depending on the frequency of the analysis visit. The analysis visit windows are defined in Table 2-1. In the tables, the days are counted since the first dose of the study treatment (i.e., Study Day 1).

When visit windows are used, all visits will be re-aligned, i.e., they will be mapped into one of the visit windows. E.g., if the *Week 4* visit of a participant is delayed and occurs on Day 46 instead of on Day 29, it will be re-aligned to visit window *Week 8*. In the case of major deviations from the visit schedule, or due to unscheduled visits, several assessments of a participant may fall in a particular visit window (either scheduled or unscheduled). Statistical approaches to handle multiple assessments in a given visit window are specified below.

In general, if two consecutive visits  $V_t$  and  $V_s$  are x days apart (t < s), when x is even, the upper limit for  $V_t$  will be  $V_t + x/2$  and the lower limit for  $V_s$  will be ( $V_s - x/2$ ) + 1; when x is odd, x/2 is rounded down to integer y, then the upper limit of the visit window for  $V_t$  will be  $V_t + y$  and the lower limit for the visit  $V_s$  will be  $V_s - y$ . The algorithm needs to ensure that visit windows are not overlapping and there are no gaps, such that each assessment can be uniquely allocated to one visit window, e.g., if Week 8 visit is scheduled at day 57, Week 12 visit is scheduled at day 85 and Week 16 visit is scheduled at day 113, then the visit window for week 12 extends from Day 72 to Day 99.

Of note, participants are allowed to have gaps in visits.

Table 2-1 Analysis visit windows

Analysis Visit	Target Day	Analysis Visit Window	Group 1	Group 2	Group 3	Group 4	Group 5	Group 6	Group 7
Baseline	1*	≤ 1	≤ 1				≤ 1	≤ 1	≤ 1
Week 1	8	2-11							
Week 2	15	12-18	2-22						2-22

Analysis Visit	Target Day	Analysis Visit Window	Group 1	Group 2	Group 3	Group 4	Group 5	Group 6	Group 7
Week 3	22	19-25							
Week 4	29	26-43	23-43				2-71		23-43
Week 8	57	44-71	44-71						44-71
Week 12	85	72-99	72-99						72-99

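### SAP 2.4.2 ends concomitant therapy at last dose + 84 days, not at the protocol's last study visit, so therapy first used late by early stoppers still in follow-up is in neither the prior nor the concomitant table

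*SAP*

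**What the plan says.** Protocol 9.2.3 (Treatments) says that a drug with at least one administration "between the day of first dose of randomized study treatment and the date of the last study visit will be a concomitant medication". It ends concomitant surgeries and procedures at the last study visit too.

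SAP 2.4.2 keeps the same start but moves the end. A medication must be given "between the day of first dose of randomized study treatment and within 84 days after last dose will be a concomitant medication", and the parallel sentence for other therapies says that those carried out "between the day of first dose of study treatment and within 84 days after last dose will be defined as concomitant non-drug therapies and procedures". Prior medications are those stopped before the first dose. The section heading also names post therapies, and SAP 5.1.3.2 has a date-imputation stub for them, but the SAP neither defines them nor plans a table of them.

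SAP Section 4 attributes changes from the protocol to early termination and refers to the change history. That history lists Section 2.4 among the updated sections. The outcome it describes is a move to descriptive analysis of the primary and secondary endpoints, followed by an unspecified later entry on details. Neither entry mentions the medication cut-off.

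On follow-up, Protocol 1.3 states: "Participants who discontinue from study treatment should still attend all visits until End of Study (EOS) as indicated in the SoA". SAP 2.5 and 2.6 summarise efficacy on the FAS, using the visit windows of SAP Table 2-1 (Week 16: Days 100–127; Week 24: Days 156–183). None of these is tied to the date of last dose.

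**The concern.** The two documents give different end dates for the same tables, and moving to a descriptive analysis does not require the change. The new end date depends on when a participant stopped dosing, whereas the PSD summaries follow the participant to Week 24. For someone who stops early and keeps attending, the therapy record used for the tables can close while outcomes are still being summarised.

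This matters because the protocol's approach is treatment policy: PSD collected after discontinuation, rescue or prohibited medication is kept. Protocol 9.3.7 itself recognises that a local steroid injection could confound the outcome under that approach, and it planned a supplementary estimand. The current SAP plans no sensitivity or supplementary analyses. The concomitant-medication and RCT-therapy tables are therefore the main planned summaries in which a reader could see whether other therapy differed between arms. A rule that leaves out late first use makes those tables incomplete for the participants who stopped early.

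**Working it through.** **Inputs**
- Dosing: "secukinumab 300 mg s.c. at Day 1 and Weeks 1, 2, 3, 4, 8, and 12" (SAP 1.1), that is Days 1, 8, 15, 22, 29, 57 and 85 in the protocol's Table 1-2.
- Visit days: "Week 8 visit is scheduled at day 57, Week 12 visit is scheduled at day 85 and Week 16 visit is scheduled at day 113" (SAP 2.4.1.1). Week 24 is Day 169 (SAP Table 2-1).
- SAP window: last dose + 84 days. Protocol window: last study visit, which is Day 169 for a participant followed to the end.

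**Check on a full course.** 85 + 84 = 169, the Week 24 visit. For on-schedule completers the two definitions agree.

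**Early stoppers who stay in follow-up**
- Cut-off = day of last dose + 84
- Gap to Week 16 = max(0, 113 − cut-off)
- Gap to Week 24 = max(0, 169 − cut-off)

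| Last dose | Day | SAP cut-off (Day) | Days uncovered before Week 16 | Days uncovered before Week 24 |
|---|---|---|---|---|
| Baseline | 1 | 85 | 28 | 84 |
| Week 1 | 8 | 92 | 21 | 77 |
| Week 2 | 15 | 99 | 14 | 70 |
| Week 3 | 22 | 106 | 7 | 63 |
| Week 4 | 29 | 113 | 0 | 56 |
| Week 8 | 57 | 141 | 0 | 28 |
| Week 12 | 85 | 169 | 0 | 0 |

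Example: with a last dose at Week 8, a therapy first used between Day 142 and Day 169 is in neither table, while the Week 24 PSD is summarised.

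These figures are for scheduled days. A late visit adds to the gap. The Week 16 window runs to Day 127, so a last dose at Week 4 can leave up to 127 − 113 = 14 days uncovered. The Week 24 window runs to Day 183, so even a Week 12 dose can leave up to 183 − 169 = 14 days.

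**Stoppers who decline further visits.** Protocol 7.1 says that for them an "end of study post-treatment safety follow up visit should be performed 12 weeks after the last administration of the study treatment". Twelve weeks is 84 days, so the two end dates roughly coincide.

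**Steroid injections that cause stopping.** The longest scheduled dosing interval is 28 days (for example, 85 − 57). An injection that leads to the next dose being withheld would normally fall within 28 days of the last dose, well inside 84, and is captured.

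**The case against.** The strongest defence is that last dose + 84 days is the SAP's on-treatment period (SAP 2.1.1.4 and 2.7) and that these tables are on the Safety Set, so matching the medication window to the adverse-event window is coherent. That is a legitimate choice for a safety display. It does not explain the departure from Protocol 9.2.3, and it leaves later first use without a category.

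A reader might infer that steroid, rescue and NSAID use before Week 16 generally disappears for early stoppers. The documents do not support that:
- At scheduled days the Week 16 gap needs a last dose at Week 3 or earlier.
- A medication counts if given at least once in the window, including one started before first dose and continued. Background NSAIDs and rescue analgesics already used before the cut-off are therefore counted under either rule.
- The tables count participants by ATC code, so an NSAID dose increase within a code would show under neither rule.
- Steroid injections that themselves trigger stopping are normally captured, as shown above.
- Nothing in the documents shows that early stoppers are the participants most likely to receive a steroid injection.

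A reader might also infer that the efficacy results are affected. They are not: PSD values are the same under both definitions, the analysis is descriptive and superiority testing is omitted.

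Some of the information may also appear elsewhere. SAP 2.3.1 tabulates every protocol deviation and lists reasons for treatment discontinuation, with no 84-day limit stated. The protocol records NSAID type changes and dose increases as deviations. This narrows the loss but does not cover permitted therapies first used late.

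**Conclusion.** The inconsistency is real and limited. SAP 2.4.2 and Protocol 9.2.3 set different end dates, and no specific reason is given. The rule affects participants who stop treatment early, remain in follow-up beyond 84 days and first use a therapy after that point. At scheduled days the uncovered period is 28 to 84 days before Week 24 for a last dose at Week 8 or earlier, and 7 to 28 days before Week 16 for a last dose at Week 3 or earlier. The consequence is incomplete description of therapy, with no change in any PSD summary.

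The documents do not give the number of early stoppers, so the number affected is unknown and could be zero. The trial was small: SAP Section 1 reports 21 randomised at termination, with patients already screened allowed to continue. If about 21 / 2 = 10.5 per arm is assumed, one omitted participant is 1 / 10.5, or roughly 10 percentage points of an arm in such a table. The final arm sizes are not stated, so this is only illustrative.

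**What to change.** In SAP 2.4.2, define concomitant medication and concomitant non-drug therapy or procedure as any given from the first dose to the last study visit, as in Protocol 9.2.3. Keep last dose + 84 days as an on-treatment flag for safety displays. The display by study period that SAP 2.4.2 already allows can separate use before and after Week 16.

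If the sponsor prefers the 84-day window, define post therapies as those first used after it, tabulate them through Week 24, and record the change and its reason in SAP Section 4.

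The first option costs two amended sentences (drugs and non-drug therapies) and a different end date in the program. No new data are needed: Table 1-2 has concomitant medications updated during the study, and Protocol 7.1 asks for new and concomitant treatments even in abbreviated contacts after discontinuation.

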## 2.5 Analysis supporting primary objective(s)

Due to the premature study discontinuation, purely descriptive analyses will be performed for the primary endpoint. Analysis of the primary endpoint will be done based on FAS.

